instructions for self-application as needed 3 times daily for pain relief. A sufficient supply of the episil® will be provided to the test subjects for the study duration. The total duration of the study per subject will be 21 days from the day of the surgical procedure. The primary outcome of postoperative pain will be determined by the subjects recording their postoperative pain threshold using a Visual Analog Scale Form/Questionnaire and the number of analgesic pills taken each day at 1, 2, 3, 5, 7, 10, 14 and 21 days postoperatively. The Visual Analog Scale Form/Questionnaire for post-operative days 1, 2, 5 and 10 will be completed at the subject's place of residence, while the Visual Analog Scale Form/Questionnaire for days 3, 7, 14 and 21 will be completed at the subject's post-operative appointments at the dental clinic. The Visual Analog Scale Form/Questionnaire will evaluate the subjects' postoperative pain using a visual analog scale (VAS) scores from 1 to 10, with 1 indicating minimal pain and 10 indicating severe pain. If no pain is present, a score of 0 will be given. The levels of postoperative pain will be classified as none to minimum if the score is "0 to 3," moderate for "4 to 6," and severe for "7 to 10." None to minimal pain will mean little or no discomfort; moderate is any pain that bothers the subject and mildly affects normal function; and severe will be considered any pain that will not be tolerated and may even disrupt the subject's daily functions.

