#### *Statistical Analysis*

Descriptive statistics will be expressed as means+/- SD and frequency distributions. Intergroup (FFG donor site using episil® and Surgicel® (test) and FGG donor site with PeriAcryl®90 and Surgicel® (control)) comparisons at 1, 2, 3, 5, 7, 10, 14 and 21 days will be analyzed by the Mann-Whitney U test. The Wilcoxon signed-rank test will be used for intragroup comparisons between 1, 2, 3, 5, 7, 10, 14 and 21 days. Differences in frequency distributions between the episil® group and the PeriAcryl®90 group will be analyzed by the Fisher exact test. Associations

between pain VAS scores and the number of analgesic pills or number of days analgesics were taken will be examined by the Pearson correlation coefficient. The significance level for rejection of the null hypothesis will be set at  $\alpha = 0.05$ .

All LDF recordings, which may be impaired by artifacts caused by the relative motion of the probe, will be excluded. An average of the 2-minute period of each individual recording will be calculated. Changes of blood flux values in the FGG donor site will be expressed as the difference ( $\Delta PU$ ) between the PU value at a specific site at a specific observation time point ( $PU_t$ ) and the individual baseline value of the same site ( $PU_0$ ):  $\Delta PU_t - PU_0$ .

Descriptive statistics will be performed using the SPSS statistical software. The  $\Delta PU$  values in the FGG donor site will be analyzed using the general linear model (GLM) univariate test, after verification of the assumptions of homogeneity of variance and normality of the residual distribution. The observation time and point and the position (mesial, center, distal and apical to the FGG donor site) will be modeled as fixed factors and the patient as a random factor with the  $\Delta PU$  as the dependent variable. The Dunnett two-sided *t*-test will be used, in order to evaluate the differences between baseline and subsequent time points and between different positions in the FGG donor site during the overall observational period. Data will be presented as mean SE. Statistical significance will be accepted at  $p < 0.05$ .

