The outcome analysis of the time needed to obtain complete re-epithelialization of the FGG donor site will be made by comparing experimental groups on the frequency distribution of patients experiencing complete re-epithelialization in each of the 4 post-operative visits. The Williams-adjusted log-likelihood ratio was performed, followed by *post-hoc* tests using Bonferroni-corrected Fisher's exact test (2-tailed).

Based on a sample size of  $n = 40$  (20 per group), a repeated measures analysis will have 80% power to detect an effect size of  $f = .57$ . For a sample size of  $n = 30$  (15 per group), the same analysis will have 80% power to detect an effect size of  $f = .67$ , while a sample size of  $n = 20$  (10 per group) will have 80% power to detect an effect size of  $f = .83$ . All of these effect sizes are classified as large effects by Cohen's guidelines (1988), or large differences in the change in pain score between the two groups.

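### The Fisher exact test, read as applying to the three ordered pain classes, ignores their order and gives up power in a secondary comparison that an ordered test would keep

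*Combined protocol and SAP*

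**What the plan says.** Postoperative pain is the primary outcome. Study Population and Design describes "visual analog scale (VAS) scores from 1 to 10, with 1 indicating minimal pain and 10 indicating severe pain" and adds: "If no pain is present, a score of 0 will be given". It then groups the scores: "The levels of postoperative pain will be classified as none to minimum if the score is" 0 to 3, with 4 to 6 counted as moderate and 7 to 10 as severe. The section does not say whether a score may be fractional, and it gives no rounding rule.

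Statistical Analysis has two between-group rules that could apply to pain. The first is that "comparisons at 1, 2, 3, 5, 7, 10, 14 and 21 days will be analyzed by the Mann-Whitney U test". The second is "Differences in frequency distributions between the episil® group and the PeriAcryl®90 group will be analyzed by the Fisher exact test". Neither sentence names its variable, and the Fisher sentence names no day. The section does not say which of the two leads. The level is given once ("The significance level for rejection of the null hypothesis will be set at" 0.05), with no multiplicity rule for pain. Re-epithelialization, the other outcome compared as frequencies, has its own procedure, which ends in a "Bonferroni-corrected Fisher's exact test (2-tailed").

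**The concern.** The three classes run from least to most pain. The hypothesis under Background, Aim, & Hypothesis is directional: outcomes should be better with episil®. The effect to look for is therefore a movement of patients from the upper classes toward the lowest.

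Fisher's test on a 2x3 table cannot see that direction. Its p-value is unchanged if the three columns are put in any other order, so a consistent move from severe to moderate to minimal earns no more credit than a scrambled pattern of the same rarity. At 20 per arm, a real shift in severity could more easily be reported as no difference in the pain classes. That result could also sit beside a significant Mann-Whitney result for the same patients on the same day, with nothing in the plan to say which one is to be believed.

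**Working it through.** **The plan's own figure.** The only power statement is 80% for a repeated measures analysis at f = .57 with n = 40. It is not for the Fisher test, and no power is given for that test. A plain two-group F test (λ = f²N = 0.57² × 40 = 13.0, df 1 and 38, α = 0.05) gives 0.94, not 0.80. The number of measures, their correlation and the tested term are not stated, so the 80% could not be reproduced from stated inputs. That is a separate matter, and nothing below rests on it.

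**Inputs from the documents.** 20 per group; α = 0.05; class limits 0-3, 4-6, 7-10.

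**Assumed inputs.** Two-sided testing; VAS roughly normal, rounded to whole numbers and limited to 0-10; SD 2.2; 2-point difference in means (d = 2/2.2 = 0.91). The documents give no mean, SD or class rate.

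**Step 1, class probabilities.** With mean μ and SD σ:
- P(0-3) = Φ((3.5 − μ)/σ)
- P(7-10) = 1 − Φ((6.5 − μ)/σ)
- P(4-6) is the remainder.

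For μ = 5: Φ(−0.682) = 0.248, 1 − Φ(0.682) = 0.248, remainder about 0.505. For μ = 3: Φ(0.227) = 0.590, 1 − Φ(1.591) = 0.056, remainder 0.354.

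**Step 2, the tests.** Each arm of 20 can fall into three classes in 22 × 21/2 = 231 ways, so there are 231² = 53,361 pairs of outcomes. For each pair, three two-sided p-values were computed, conditional on the class totals m₁, m₂, m₃:
- Fisher (Freeman-Halton): sum of the probabilities of all tables no more probable than the one observed.
- Exact ordered test (Wilcoxon-Mann-Whitney on the classes): sum of the probabilities of all tables whose midrank sum W is at least as far from its mean.
- Approximate ordered test: z = (W − E[W])/√V, with V = (20²/12) × [41 − Σ(m³ − m)/(40 × 39)].

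Power is the sum, over all pairs with p ≤ 0.05, of P(control outcome) × P(test outcome).

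**Step 3, results.**

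| Mean VAS, control to test | Fisher | Exact ordered | Approximate ordered | Loss vs exact | Loss vs approximate |
|---|---|---|---|---|---|
| 5 to 3 | 55.9% | 65.6% | 69.4% | 9.7 | 13.5 |
| 4 to 2 | 50.5% | 58.6% | 64.2% | 8.1 | 13.7 |
| 6 to 4 | 57.8% | 67.0% | 71.1% | 9.2 | 13.3 |

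The Mann-Whitney test on the 0-10 scores themselves has about 76-77% power in these settings (4,000 simulated trials each).

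**Step 4, is the gain only a looser test?** With no difference, the rejection rates are 4.3-4.4% for Fisher, 3.9% for the exact ordered test and 5.0% for the approximate one. The exact ordered test is stricter than Fisher and still gains 8-10 points, so that gain comes from order. The further 4-6 points of the approximate test (for example 69.4 − 65.6 = 3.8, and 64.2 − 58.6 = 5.6) reflect less conservatism.

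**Step 5, wider assumptions.** Control mean 3-7, SD 2-3, 20 per arm:

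| d | Fisher power | Loss vs exact | Loss vs approximate |
|---|---|---|---|
| 0.5 | 15-20% | 0.9-5.4 | 7.6-8.9 |
| 0.91 | 40-58% | 1.8-10.0 | 12.7-14.8 |
| 1.14 (2 × 0.57) | 56-79% | 1.8-7.9 | 9.0-15.2 |
| 1.3 | 66-89% | 1.6-7.0 | 5.6-14.0 |

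The loss is always in the same direction. Its size depends on the assumed means and SD and on which ordered test is the comparator.

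**Step 6, class limits.** Whole numbers 0 to 10 each fall in exactly one class. At a resolution of 0.1, the readings 3.1-3.9 and 6.1-6.9 (9 + 9 = 18) would fall in none. That is 18 of 101 readings on a full 0-10 line, or 18 of 92 if the scale is 0 plus 1.0-10.0 (1 + 91).

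**The case against.** The strongest reply is that the target is inferred. The Fisher sentence could mean a yes/no variable, such as any pain (the Background reports pain as an incidence) or any analgesic use. For a 2x2 table the point about order disappears. This stands as a caution. The three classes are nevertheless the only pain categories that the plan defines, and re-epithelialization is provided for separately. If something else was meant, the plan needs to name it.

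Second, the efficient analysis is already planned. The Mann-Whitney test at all eight days, apparently on the VAS, uses order and has more power than any test on the classes. This largely stands: detection of a shift in pain does not depend on the class table. The plan does not rank the two tests, however, so the class result could still be given equal weight.

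Third, Fisher is valid at this sample size. That stands in full: the cost is power, not type I error.

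Two stronger readings are tempting. A reader might take 12-13 points, or any single figure, as the fixed loss. The documents give no SD or class rates to support one, and losses of that size arise only against the approximate test. A reader might also conclude that the class limits leave scores between 3 and 4 and between 6 and 7 unclassified. That follows only if fractional scores are recorded, which the documents do not say.

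**Conclusion.** The point holds on the natural reading that Fisher is applied to the three pain classes. At 20 per arm, SD 2.2 and a 2-point shift, ignoring order costs 8-10 points of power against an exact ordered test on the same classes, and 13-14 against a tie-corrected approximate one. Across control means of 3-7, SDs of 2-3 and d of 0.5-1.3, the range is about 1-10 and 6-15 points. All of these rest on assumed VAS distributions.

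The consequence is limited. The loss falls on what appears to be a secondary comparison of data that the Mann-Whitney test already covers with order. The change is worth making because it is nearly free, but the trial's conclusion on pain does not hang on it. The class limits are an ambiguity to clear up, not a demonstrated gap.

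**What to change.** In Statistical Analysis:

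1. Name the variables and days to which the Fisher test applies.
2. For the three pain classes, replace Fisher with an ordered test (exact Wilcoxon-Mann-Whitney or linear-by-linear). Alternatively, present the classes descriptively and say that the Mann-Whitney test on the VAS carries the inference.
3. Keep Fisher for yes/no variables.

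In Study Population and Design, as a minor clarification, state that whole-number scores are recorded. If fractional scores are possible, define the classes without gaps (for example 3 or less, above 3 to 6, above 6).

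The cost is a few sentences of wording, settled before the data are analysed by group. No new data or visits are needed.

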#### *Surgical Procedures & Postoperative Care*

As stated above, periodontal residents under the direct supervision of periodontal faculty will perform the FGG procedure in all subjects. The FGG procedure will be performed following the surgical technique of Sullivan and Atkins or Miller. The donor tissue for the FGG procedure will be retrieved from either the right or left side of the palate. The FGG donor sites will be of a standardized size of 10 mm x 10 mm. As stated above, subjects in the control group will receive a hemostatic gauze, Surgicel®, covered by a cyanoacrylate dressing, PeriAcryl®90, at the donor site while the subjects in the test group will receive the same brand of hemostatic gauze, Surgicel®, but covered with episil®. Subjects in the test group will be given the remainder of the bottle of episil® with instructions for home application up to 3 times daily. Postoperative instructions will include discontinuing tooth brushing and flossing around the surgical site for the first 3 post-operative weeks. Subjects will be provided with a prescription for ibuprofen (600 mg) to take as needed for analgesia, unless contraindicated. Acetaminophen with 30mg of codeine will be prescribed to subjects unable to ingest ibuprofen.

The LDF measurements in the FGG donor site and on the contralateral side of the palate will be recorded in four sites. A clear acrylic stent will be fabricated for each subject from individual subjects' dental casts. Holes will be made in the stent in four locations on each the right and left sides of the palate. One site located centrally, one close to the mesial, one close to the distal and one close to the apical of the FGG donor site and in the same locations on the contralateral side of the palate will be measured at each of the specified postoperative appointments. The LDF measurement will be performed at baseline prior to surgery, immediately after harvesting of the FGG donor site, and on post-operative days 3, 7, 14 and 21. The LDF measurements will be performed with the tip of the fibre optic probe inserted into the holes of the individual acrylic stent. The LDF probe will be placed at a

standardized location perpendicularly to the tissues and at a distance of 0.5 mm from the tissues and will remain motionless during the LDF measurements.

Below is a summary of the timeline of the study:

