**First clinic visit (Screening visit):** Discussion of study and attain informed consult for participation in the study; medical history will be updated, vital signs will be taken, and an upper arch alginate impression will be taken in order to create a plastic stent, which will be worn during the laser Doppler flow measurements.

**Second clinic visit (Day of Surgery):** The day of surgery, the laser Doppler flowmetry readings will be performed before the surgery and then again immediately after harvesting of the FGG donor site. Subjects will receive 4 copies of the Visual Analog Scale Form/Questionnaire to be completed at their homes on days 1, 2, 5, and 10 postoperatively, which will be labeled accordingly. Subjects assigned to the test group will receive a manual-metering pump containing sufficient episil® for the duration of the study. Subjects in the test group will be instructed to use the pump up to 3 times a day. Instructions for home application of the episil® will be given orally and in writing at this appointment.

**Day 1 post-operative:** All subjects will complete at home the Day 1 Post-Operative Visual Analog Scale Form/Questionnaire.

**Day 2 post-operative:** All subjects will complete at home the Day 2 Post-Operative Visual Analog Scale Form/Questionnaire.

**Day 3 post-operative (3rd clinic visit):** All subjects will bring the 2 completed Visual Analog Scale Forms/Questionnaires to the day 3 post-operative clinic appointment and will complete the Day 3 Post-Operative Visual Analog Scale Form/Questionnaire during this appointment. The laser Doppler flowmetry readings will be performed on the free gingival graft donor site and on the contralateral side of the palate utilizing the fabricated stent with holes for the Doppler probe positioning for repeatability of readings. 3% H2O2 will be applied to the FGG donor site with a syringe and the appearance of bubbles will be recorded as a dichotomous variable.

**Day 5 post-operative:** All subjects will complete at home the Day 5 Post-Operative Visual Analog Scale Form/Questionnaire.

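### VAS is to be correlated with days of analgesic use, but the recording described covers only 8 of the 21 postoperative days, so that day count is undercounted and uneven

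*Combined protocol and SAP*

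**What the plan says.** The Statistical Analysis section examines associations between VAS pain scores and the "number of analgesic pills or number of days analgesics were taken", using the Pearson correlation coefficient. It does not say how the day count is to be derived.

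The recording schedule is in Study Population and Design. Alongside VAS, subjects record "the number of analgesic pills taken each day at 1, 2, 3, 5, 7, 10, 14 and 21 days postoperatively". Follow-up is three weeks: "The total duration of the study per subject will be 21 days from the day of the surgical procedure".

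The visit timeline in Surgical Procedures & Postoperative Care describes the forms. On the day of surgery each subject receives "4 copies of the Visual Analog Scale Form/Questionnaire to be completed at their homes on days 1, 2, 5, and 10", one labelled for each day. For the other four days, the "Form/Questionnaire for days 3, 7, 14 and 21 will be completed at" the clinic appointments. That makes eight forms, each tied to one day.

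Analgesics are not on a fixed schedule. Subjects get a "prescription for ibuprofen (600 mg) to take as needed for analgesia, unless contraindicated", and those who cannot take ibuprofen get an alternative.

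**The concern.** Counting the days on which a subject took analgesics requires knowing, for every day, whether any were taken. The forms described give that for eight days and are silent on the other thirteen. An analyst following the plan would have to choose a substitute after the data are in: a count of recorded days, interpolation between forms, or the last recorded day of use. These can give different values for the same subject.

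The obvious substitute, the count of recorded days, is a poor measure of how long analgesics were needed. It is fine-grained in the first days and coarse afterwards. If it were reported under the plan's label, readers would take it for true days of use.

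**Working it through.** **Inputs.** Recording days S = {1, 2, 3, 5, 7, 10, 14, 21} and a 21-day follow-up (Study Population and Design); one form per listed day (visit timeline); as-needed analgesics (Surgical Procedures & Postoperative Care).

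**Step 1: coverage.** Recorded: 8/21 = 38.1%. Not recorded: 13/21 = 61.9%, namely days 4, 6, 8, 9, 11–13 and 15–20. Coverage is front-loaded: 5 of the first 7 days, but 3 of the last 14.

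**Step 2: direction of error.** Let U_d = 1 if analgesics were taken on day d, and 0 otherwise. True days T = sum of U_d over days 1–21. Recorded days R = sum of U_d over S. Then T − R is the sum of U_d over the 13 unrecorded days. It is never negative, so R cannot exceed T, and R cannot exceed 8.

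**Step 3: continuous use from day 1 (assumed).** If the last day of use is k, R is the number of days in S up to k.

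| Recorded count | True days that fit |
|---|---|
| 0 | 0 |
| 1 | 1 |
| 2 | 2 |
| 3 | 3–4 |
| 4 | 5–6 |
| 5 | 7–9 |
| 6 | 10–13 |
| 7 | 14–20 |
| 8 | 21 |

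Only 0, 1, 2 and 21 days are identified exactly. Two subjects at 14 and 20 days differ by 6 true days and 0 recorded days. Two at 7 and 14 days differ by 7 true days and 2 recorded days.

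**Step 4: intermittent use.** As-needed use does not have to be continuous. Six true days on days 1, 2, 3, 5, 7 and 10 give R = 6. Six true days on days 4, 6, 8, 9, 11 and 12 give R = 0.

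**Step 5: consequence for the correlation.** The documents give no data on analgesic use, so this step rests on simulated patterns. For continuous use, the last day was Poisson with a gamma-distributed mean (shape 3), capped at 21. For intermittent use, the daily probability was exp(−d/t), with t gamma-distributed (shape 3).

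| Pattern | True mean days | Recorded mean days | Correlation of R with T | Share with R = T |
|---|---|---|---|---|
| Continuous, mean 3 | 2.99 | 2.40 | 0.957 | 66% |
| Continuous, mean 5 | 5.00 | 3.42 | 0.945 | 40% |
| Continuous, mean 7 | 6.96 | 4.20 | 0.942 | 26% |
| Continuous, mean 10 | 9.68 | 5.09 | 0.947 | 14% |
| Intermittent, mean t = 3 | 2.51 | 1.79 | 0.884 | 58% |
| Intermittent, mean t = 5 | 4.25 | 2.63 | 0.860 | 33% |
| Intermittent, mean t = 8 | 6.45 | 3.52 | 0.845 | 15% |

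The count itself is often wrong, and its mean falls well short of the truth when use is longer. The ranking of subjects survives better, with correlations of about 0.94–0.96 for continuous use and 0.85–0.88 for intermittent use. Pearson's r is unchanged by linear rescaling, so it suffers less than the day count.

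**The case against.** The strongest objection is that the questionnaire is not in the documents, and the schedule's wording is open to a second reading: daily use, reported at eight time points. If the form asks about each day since the last one, the gap closes. This stands as a condition. The more natural reading is pills on the listed days only, and nothing in the text states a look-back. If there is one, the protocol should say so.

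Three stronger conclusions are tempting, and the documents do not support them.

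- *That the primary outcome is compromised.* Study Population and Design does place pill numbers within the primary outcome, but on the eight listed days, where they are scheduled to be recorded. The count of days of use is not in that definition. It appears once, as one of two alternatives in an association analysis. Nor is a 21-day pill total stated: the pill number can be paired with VAS on the same eight days.
- *That a treatment difference in duration of analgesic need would be lost.* No between-arm test of duration is named, so this would matter only if one were added or reported.
- *That every version of the count is distorted.* The recorded count is right for subjects with no use or with use only on days 1–3, and continuous use can be bounded to an interval.

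It is also fair to say that the Background places the pain problem mainly in the early period and first week, where 5 of 7 days are recorded. The contrasts at 10 to 20 days assume use into the second and third weeks, which the documents neither show nor exclude.

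**Conclusion.** The point holds, within limits. As described, the records cover 8 of 21 days. Unless the unseen questionnaire asks about the days between forms, the true number of days of analgesic use cannot be obtained for most patterns of use beyond day 3. A count of recorded days errs only downward and has unequal steps. The interval widths (up to 14–20 days for one score) assume continuous use from day 1; as-needed use can make the error larger.

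The damage is confined to one supporting association, and under the assumed patterns the correlation is weakened rather than destroyed. The day-specific VAS comparisons and the pill counts on the eight listed days are unaffected. The change is still worth making: the analysis cannot be run as worded from the recording described, and the remedy is cheap.

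**What to change.** Add a daily pill tally for days 1 to 21 to the take-home form, collect it at the existing day 3, 7, 14 and 21 visits, and state in Statistical Analysis that days of use is the number of tally days with at least one pill. This raises coverage from 8/21 to 21/21. The cost is one line per day on a form and a slight extra burden on subjects; visits and sample size do not change.

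If the forms cannot change, redefine the variable as *number of the 8 recorded days with analgesic use* and do not interpret it as duration of use. That costs only wording, but leaves the uneven scale in place.

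If the questionnaire already asks about the days between forms, say so in Study Population and Design and give the derivation.
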